FIOC was designed specifically to aid development of positive coparenting alliances between at-risk (unmarried, uncoupled, low income) African American mothers and fathers having a first baby together. In the RCT, randomly-assigned control group families (referred by already-known referral agents and partners who worked closely with our team on the pilot projects) will receive Pinellas County services as-usual for pregnant parents and assistance of a Resource and Referral Navigator for referrals to desired community services ("Treatment as Usual", or TAU). The remaining (experimental group) families will receive the same services and aid, plus the 6-session FIOC prenatal intervention with a post-natal booster session. The first 150 families consented in will be assigned to groups via urn randomization. The remaining families recruited up to 170 will be assigned to the experimental (FIOC) group to achieve balance in the number of families contributing postnatal follow-up data longitudinally in the two groups to allow minimally sufficient statistical power for analyses. The FIOC intervention addresses the importance of safe, healthy families for early infant development, the impact a cooperative and sustained coparenting alliance can have in promoting positive infant development, challenges unmarried parents face cultivating a coparenting alliance together when their commitment to one another as romantic or married partners is in doubt, and ways to surmount these obstacles, maintain rapport, and sustain a strong alliance.

All 170 participating families, both at intake (prior to the intervention) and then again at 3 and 12 months post-partum, will report beliefs about fatherhood; extent of depressive symptomatology; and quality of the mother-father partnership. State-of-the-field coparenting observations will be conducted at each follow-up, along with measures of parental stress, intimate partner violence (IPV), perceived coparenting support, father engagement, and infant socioemotional adjustment. Analyses will examine impact of the intervention on promoting more supportive, coordinated post-partum coparenting alliances and more positive adult and infant outcomes. Exploratory analyses will examine links between father involvement and child adjustment and whether this coparenting intervention also stands to prevent IPV.

2. Background information

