- Aim 1: To determine the efficacy of FIOC in positively affecting first-year coparenting of unmarried African American parents, relative to early coparenting of comparison families
Hypothesis 1: Families who participate in FIOC will demonstrate more cooperation and better communication in their post-natal coparenting systems at 3 and 12 months post-partum than families receiving TAU
- Aim 2: To determine the efficacy of FIOC in affecting first-year parental adjustment.
Hypothesis 2: Mothers and father who participate in FIOC will show greater decreases in depressive symptomology from prenatal to postnatal assessments than parents receiving TAU.
Hypothesis 3: Mothers and father who participate in FIOC will show lower levels of parenting stress at 3 and 12 months than families receiving TAU.
- Aim 3: To determine the efficacy of FIOC in affecting early child outcomes.
Hypothesis 4: Infants whose coparents participate in FIOC will show a more advanced

triangular capacity at 3 and 12 months

Hypothesis 5: Infants whose coparents participate in FIOC will show better regulatory and socioemotional competence at 12 months than control group children.

- Aim 4: To determine the efficacy of FIOC in affecting father involvement
Hypothesis 6: Fathers who participate in FIOC will show greater involvement at 3 and 12 months post-partum
- Aim 5: To determine whether increased father involvement is associated with better socioemotional adjustment by the baby
Hypothesis 7: Children of more involved fathers will show greater regulatory and socioemotional competence at 12 months post-partum
- Aim 6: To explore whether the FIOC intervention has an impact on the emergence of intimate partner violence (IPV)
Hypothesis 8: IPV will be more likely to emerge during the child's first year among TAU families than among families who complete the FIOC intervention
- Aim 7: To determine whether enrollment numbers, randomization rates, retention rates, and comparative RCT outcomes differ as a function of active versus passive recruitment methods for unmarried mother-father dyads.
Hypothesis 9: Proportions of enrollment and randomization and retention rates will favor families identified via self-referral (passive recruitment), while outcomes for families completing the intervention will not differentiate the two groups.

4. Study design including information needed to answer the research questions:

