- 2. [name].**, Co-P.I. Provide oversight of all clinical aspects of project related to IPV assessment and safety planning, including training of assessment staff and Mentors and oversight of randomization of cases with IPV or other mental health issues; monitoring of clinical operations, clinical consultation, filing for mandatory reporting, direction of safety monitoring team, and compliance of all staff with clinical protocols. Attend senior staffings and other relevant meetings.

9. The risks to the subjects:

While this is considered to be a minimal risk study, there is always the possibility of adverse effects resulting from participation. These include:

1. possible violation of confidentiality,
2. possible discomfort due to assessment procedures,
3. possible embarrassment in disclosing sensitive personal information,
4. possible disclosure of information about intended physical harm to victims or abuse/neglect of children that would need to be reported to the child welfare agency and an investigation of the allegations(s) and further action, as indicated, that could ensue,
5. possible disclosure of homicidal or suicidal thoughts, threats, ideation, attempts, or plans requiring mandatory reporting if participants are at imminent risk of endangering themselves or others.
6. possible dissatisfaction with the assessment/intervention procedures

Procedures for managing risks are described below.

10. Any experimental procedures including the use procedures already being performed on subjects for diagnostic or treatment purposes.

All participants will take part in the curriculum (6- pre-natal sessions and 1 post-natal session) designed to support families and strengthen coparenting relationships across the transition to new parenthood. Participation in the intervention is the only experimental procedure used in this project. The assessments families will complete have all been previously used by the PI and other family researchers in studies with similar populations.

11. The potential benefits to subjects:

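### The outcome clause of Hypothesis 9 compares recruitment routes only among FIOC completers, so it cannot answer the comparative-outcomes part of Aim 7, which needs both arms

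*Protocol*

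**What the plan says.** Aim 7 (Protocol, section 3) has four components: numbers enrolled, randomisation rates, retention rates, and whether "comparative RCT outcomes differ as a function of active versus passive recruitment methods for unmarried mother-father dyads". Hypothesis 9, attached to that aim, predicts that the rates will favour self-referred families and that "outcomes for families completing the intervention will not differentiate the two groups". The two groups in that sentence are the recruitment routes.

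Section 1 separates the arms. Control families "will receive Pinellas County services as-usual for pregnant parents" and have help from a Navigator. Experimental families receive the same, "plus the 6-session FIOC prenatal intervention with a post-natal booster session". Section 4 describes the same division. Hypothesis 8 confirms what completion means, because it contrasts IPV "among TAU families than among families who complete the FIOC intervention".

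One sentence points the other way. Section 10 states: "All participants will take part in the curriculum (6- pre-natal sessions and 1 post-natal session". That contradicts sections 1 and 4, and the passages must be reconciled. It does not turn TAU families into completers.

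The SAP covers Aims 1 to 4 and two exploratory aims (father engagement and IPV). It contains no analysis by recruitment route.

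**The concern.** The aim and its hypothesis place the same question on different populations. A FIOC-versus-TAU comparison by route needs TAU families from both routes. A comparison among intervention completers contains no TAU family and also drops FIOC families who stop early. It shows whether completers from the two routes end at similar levels, not whether FIOC helps both kinds of family equally.

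Completion is also decided after assignment and may depend on route. The first half of Hypothesis 9 expects retention to favour self-referred families. If completion follows retention, which is an inference, the second half conditions on something the protocol itself expects to differ between the groups being compared.

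At stake is a statement of no difference by route that the data behind it could not support. Section 7 of the protocol says the results will inform whether a multi-site trial is worthwhile. That such a statement would also shape how that trial recruits is a plausible further step, but the protocol does not say so.

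**Working it through.** **The plan's own figure.** Section 5 gives 60 families per arm after attrition, F(1, 117) = 7.74 with d = .514 at power .8, and F = 4.03 with d = .37 at power .5. Using d = 2 × sqrt(F/117):
- 2 × sqrt(7.74/117) = 0.514
- 2 × sqrt(4.03/117) = 0.371

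Both reproduce, and a two-sample calculation with 60 per arm and d = .514 gives power 0.80. These figures are for the two-arm comparison. The plan gives no sample size, power or margin for Aim 7.

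**What each statement targets.** Write P for passive and A for active, and let each term be a mean outcome.
- Aim 7: (FIOC − TAU among P) − (FIOC − TAU among A) = (FIOC P − FIOC A) − (TAU P − TAU A).
- Hypothesis 9: (FIOC P − FIOC A), in completers only.

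Take the case most favourable to Hypothesis 9: every FIOC family completes and the first bracket is exactly 0. The effect difference by route is then minus the TAU gap:

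| TAU P − TAU A (SD) | FIOC P − FIOC A (SD) | Difference in FIOC effect, P − A (SD) |
|---|---|---|
| −0.50 | 0 | +0.50 |
| −0.25 | 0 | +0.25 |
| 0 | 0 | 0 |
| +0.25 | 0 | −0.25 |
| +0.50 | 0 | −0.50 |

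Hypothesis 9 would be judged correct in every row. As an illustration only, suppose the effect in active families equals the detectable d of .514 and self-referred TAU families do 0.3 SD better than other TAU families (an assumed gap). The effect in self-referred families is then .514 − .30 = .214, which is .30/.514 = 58% smaller, and Hypothesis 9 still holds.

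**Precision of the matching contrast.** The documents give no counts by route, so these inputs are assumptions.
- Retained randomised families: 150 × 120/170 = 106, or 53 per arm. This applies the section 5 ratio of analysed to enrolled families and assumes an even split.
- Passive share: about 15% or 30%, the same in both arms.
- Outcome SD = 1. SE = sqrt(2/n_A + 2/n_P), with n_A and n_P counted per arm. 95% half-width = 1.96 × SE.

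| Active, passive per arm | SE | 95% half-width (SD) |
|---|---|---|
| 45, 8 (about 15%) | sqrt(2/45 + 2/8) = 0.54 | 1.06 |
| 37, 16 (about 30%) | sqrt(2/37 + 2/16) = 0.42 | 0.83 |

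With the full 60 per arm of section 5, the interaction detectable at 80% power is 1.43 SD with 15% passive and 1.02 SD with 50% passive. Power for an interaction of 0.514 SD is 17% and 29% respectively.

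**Who is randomised.** Section 1 randomises the first 150 families and assigns the rest, up to 170, to FIOC: 170 − 150 = 20 families. Appendix A describes a campaign tied to Aim 7 that sought 20 to 25 participants to finish enrolment. Some self-referred families may therefore sit in the non-randomised block. This is an inference, since no counts by route and arm are given.

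**The case against.** The strongest reply is that Hypothesis 9 is a one-sentence prediction, not a specified test, and that its completer wording may be loose shorthand. Hypothesis 8 also speaks of families who complete FIOC, yet the SAP analysis for it compares the two conditions with no restriction to completers. That is fair: nobody should infer that the sponsor has chosen a completer analysis set for Aim 7. But for Hypothesis 8 the SAP supplies a two-arm comparison, and for Aim 7 it supplies nothing. Even if the phrase means every family assigned to FIOC, the comparison remains one-armed.

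The phrase about comparative outcomes could also mean outcomes simply compared between routes. That is the weaker reading in a trial of FIOC against TAU, and restricting it to completers would still leave out every TAU family.

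A reader might go further and infer that Aim 7 as a whole cannot be answered. The documents do not support that: three of its four components do not depend on completing FIOC. Nor are TAU families without outcomes. Section 1 plans assessments of all 170 families at 3 and 12 months, so the two-arm contrast needs no new data.

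Finally, the matching contrast is imprecise and could not establish equal effects by route. That stands, and it limits what the fix can deliver. It does not make the one-arm comparison informative about treatment effect.

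**Conclusion.** The point holds for the outcome clause of Hypothesis 9 set against the comparative-outcomes component of Aim 7, and no further. On the natural reading of Aim 7 the mismatch is one of identification: a null result among completers is compatible with any effect difference by route. That conclusion needs none of the assumed numbers. It rests only on TAU families not receiving FIOC, as sections 1 and 4 state.

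The sizes are conditional. The fall from .514 to .214 is an illustration built on an assumed 0.3 SD gap, and .514 is the plan's detectable effect, not an effect it expects. The half-widths of about 0.8 to 1.1 SD rest on the assumed retention and passive shares. The interval would be wider still if few self-referred families were randomised. Aims 1 to 6 are untouched.

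**What to change.** Reword the outcome clause of Hypothesis 9 so that it refers to the difference in the FIOC-minus-TAU effect between active and passive families. Add the matching analysis to the SAP: an arm-by-route term in the randomised families (the first 150) with outcome data, by assigned arm regardless of sessions completed, reported with a 95% CI and labelled descriptive. Report counts by route and arm, with randomised and directly assigned families shown separately, so that the reader can see how many self-referred families inform the term. Any completer comparison should be kept apart, as a separately labelled description of FIOC families only.

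The cost is wording in both documents, one model term and one table, using data already planned for collection. The downside is that the interval will be wide, so no claim of equal effect by route can be made.

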randomization, to maximize the likelihood that treatment groups will be balanced with respect to demographic variables (presence of children from prior unions) and prognostic variables (frequency of IPV). We will use a Microsoft Access-based program previously developed for the Yale Department of Psychiatry NIDA-funded Psychotherapy Development Center and used in prior studies by Co-PI [name]. In urn randomization, an algorithm modifies ongoing randomization probabilities based on prior composition of treatment groups, and maximizes multivariate equivalence of treatment groups (Stout et al., 1994). Thus, urn randomization offers the benefits of balancing allocation of important prognostic variables in treatment groups, while still retaining other benefits of random assignment (Wei, 1978).

Once enrolled, parents assigned to the treatment group are contacted by the Intake Coordinator or Resource and Referral Navigator who introduces their mentors and delivers the participants' gift cards for completing the intake assessment. Mentors arrange two initial 1-on-1 mentorship sessions with the parents, as per the FIOC protocol, after which the FIOC intervention commences. Families randomized to the control group are contacted by the Intake Coordinator or Resource and Referral Navigator, who schedules a meeting to deliver gift cards for completing the intake assessment. The R&R Navigator also provides a listing of existing Pinellas County Services and offers parents the opportunity to contact her at any time for assistance with referrals to Pinellas County services for pregnant or parenting families. All families, regardless of assignment, are also reminded about the follow-up assessments that will be completed at 3 months post-partum; and at 12 months post-partum. A formal check-in will be completed at 1-month post-partum (Congratulations on the birth card sent), and episodic newsletters and reminder texts (for families consented after January 30, 2017) will be sent at staged intervals to help keep in touch. Texts or phone calls to keep in touch will be sent to female participants by female staff only to ensure comfort of research participants.

All study participants will be offered the opportunity to be seen for initial assessments, follow-ups and mentoring sessions in person or via the Microsoft Teams platform.

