For families who will be seen via the telehealth option, mothers will have an additional meeting with the resource person prior to the assessment in order to ensure safety and comfort with proceeding in the study via telehealth.

The project timeline and work plan are projected as follows:

Work Plan Timeline

Major Activities per 6 Month (Years 1-5)	1-6	7-12	13-18	19-24	25-30	31-36	37-42	43-48	49-54	55-60
Recruitment/Baseline Assessments (T1)										
Prenatal FIOC Intervention										
3 Month Assessments (T2)										
12 Month Assessments (T3)										
Analysis, Reports										

The table below summarizes major constructs of interest and timeline of administration. This is followed by summary descriptions of all measures. Individual scales and measures are embedded within an interview protocol. Response keys accommodate parents with poor reading

levels. In terms of participant burden, demographic and risk interviews (with surveys) average 45 minutes; mother-father coparenting discussions (with debriefing) average 20 minutes, and postnatal LTP assessments average 10 minutes inclusive of directions.

Data Collection Measures, Schedule, and Respondent

Measure	Mother			Father			Baby	
	B	3P	12P	B	3P	12P	B	3P
Risk History	X			X				
IPV (Conflict Tactics Scale)	X	X	X	X*	X*	X*		
Beliefs about Fathering	X	X	X	X	X	X		
The Role of the Father Questionnaire	X	X	X	X	X	X		
Depressive Symptoms	X	X	X	X	X	X		
Positive and Negative Quality Relationships Scale	X	X	X	X	X	X		
Collaboration/conflict (Coparenting Discussions)	X	X	X	X	X	X		
Parenting Stress Index		X	X		X	X		
Parenting Alliance Measure		X	X		X	X		
Coparenting during the LTP		X	X		X	X		
Father Engagement		X	X		X	X		
Infant Triangular Capacities (LTP)								X
Infant Socioemotional Development (BITSEA)			X			X		
Child Health Background Questionnaire			X					

Note. B=Baseline; 3P=Post-Partum, 12P=12 months Post-Partum

*Father is only administered the IPV screen/CTS2 at baseline if mother does not report certain levels/traits of violence, as specified in the IPV manual, on her IPV screen at baseline. Father is only administered the IPV screen/CTS2 at post assessment time points if he was administered the IPV screen/CTS2 at baseline.

Measures

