6. Mother-Father Conflict and Collaboration during Coparenting Discussions. Evaluated using a paradigm validated in the PI's prior coparenting studies. Father and mother discuss areas of current child-related disagreement or uncertainty (e.g., overnights; paternal support; childcare; child temperament concerns; involvement of other kin caregivers; complications of children from prior unions). Raters observe and rate videotaped discussions using Lindahl and Malik's (2000) System for Coding Interactions in Dyads (SCID). In the feasibility study, statistically-significant improvements were seen in SCID ratings of (increased) problem-solving communication; (increased) mother-father cohesion; and (decreased) coerciveness

Outcome Variables: Family and Child Measures Taken at Times 2 and 3 Only

1. Parenting and Coparenting Adjustment. Two sets of coparenting indicators and one parenting measure not yet possible to evaluate at Time 1 will be obtained as Time 2 and 3 outcome measures:

a) Coparenting: Felt Coparenting Support: Reported by both mothers and fathers, and assessed using Abidin and Konold's (1999) 20-item Parenting Alliance Measure (PAM). The PAM is a five-point self-report scale (1 = strongly disagree; 5 = strongly agree), which evaluates how cooperative, communicative and mutually respectful parents are with regard to caring for the baby.

b) Coparenting: Observed Coparenting Behavior during Trilogue Interaction. All families are assessed at 3-months and at 12-months post-partum in Fivaz-Depeursinge and Corboz-Warnery's Lausanne Trilogue Play. The LTP has 4 parts: (a) first one parent plays with baby, other parent just present; (b) parents switch roles; (c) all 3 family members play together; (d) parents active and baby placed in the third party position. Coparenting during the LTP at 3 months postpartum is to be evaluated using the 3-month version of the Coparenting and Family Rating System (McHale & Coates, 2015). The standard CFRS is to be used to evaluate 12-month coparenting during the LTP.

c) Degree of Parenting Stress: Reported by both mothers and fathers, and assessed using a 36-item Parenting Stress Index-Short Form, validated in a low-income, African American population (Reitman et al. 2002). The PSI-SF has 36 items from the original 120-item PSI. Items are identical to those in the original version and yields scores on the following subscales: 1) Parental Distress, 2) Parent-Child Dysfunctional Interaction, and 3) Difficult Child

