2. Father Engagement:

a) Father engagement is assessed using relevant items from the HAPPI (Cabrera et al., 2004). The HAPPI father-child engagement activities scale consists of 34 items on which the respondent reports the frequency with which various activities by the father with the child (socialization, management, didactic, physical play/warmth, and caregiving) took place over the past month. Questions are answered on a Likert-type scale from 1 (more than once a day) to 6 (not at all).

b) Multiple measures introduced by the Fatherhood Research and Practice Network (FRPN) are also being used to estimate father engagement, coparenting decision making, and barriers to involvement at 3 and 12 months post assessment. Scales include the Fatherhood Research and Practice Network's Father Engagement Scale (FRPN-ES, completed by fathers only), Maternal Gatekeeping Scale (completed by mothers only), Measure of Father's Challenges (completed by fathers only) and Decision Making Responsibilities Scale (completed by both parents). Besides frequency of engagement, items from the HAPPI completed by both parents will be used to estimate father accessibility at both 3 and 12 month post assessment.

c) The Father Involvement Scale (Hernandez & Coley, 2007) is comprised of a series of queries assessing fathers' accessibility, responsibility, and involvement with the child.

3. Infants' Triangular Capacities. Infants' deployment of attention and affect during the LTP interactions with their parents at 3 and at 12 months will be rated as follows:

a. Gaze: Gaze frequency and duration (at mother's face, at father's face, elsewhere) will be coded.

- b. Affective configurations: Coding of affective configurations during periods of gaze at either parent, coded as social engagement, social monitoring, tense monitoring, active protest or non-engagement.
- c. Triangular bids: The term ‘bid’ covers infant response to parental solicitations as well as initiative by the infant. Four categories are coded: triangular engagement, triangular monitoring, triangular tension, and triangular protest.

4. Child Health Background. Child’s health history during the first year of life will be assessed via a short self-report questionnaire.

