Appendix A
Community Recruitment Activities (Scope of Work)
Completed by Community Development & Training Center (CDAT)
During Fall/Winter 2019-20
Responsive to Specific Aim 7 of USF's NIH-sponsored FIOC project

Community Development & Training Center (CDAT) will lead a collaborative media and marketing campaign to reach potential participants for the University of South Florida's NIH-supported "Figuring it Out for the Child" (USF FIOC) Program. The campaign will leverage the marketing reach and organizing capacity of several partner organizations, combined with the USF FIOC network of existing community contacts, to implement a comprehensive approach. Media partners to the campaign will include the following:

- The New Image Project
- Tampa Bay Breakfast Club
- The Power Broker magazine
- TheBurgVotes.com
- The Weekly Challenger Newspaper
- The Bulletin Newspaper
- On the Beat St. Pete
- 96.3 FM (radio)
- 99.1 FM (radio)

The campaign's scope of work will include the following:

- CDAT's production of creative content including graphic designs (infographics, memes, and advertisements) and video interviews with parents who participated in the FIOC program and expressed their satisfaction with the program and their openness to being recontacted.
- Print ad placements
- Digital ad placements
- Social media ad placements
- On-air radio interviews and special programs
- Facebook Live interviews and special programs
- Print & digital articles (shared via social media)
- Outreach for and facilitation of a Final Push Luncheon with Key Partners (targeting attendance by 50 partners and prospective partners and 4 media outlets)

The campaign will operate from October 23, 2019 through March 1, 2020. New graphic content generated will be submitted for approval by Amendment through USF's Internal review Board. The goal of the campaign is to generate as many as 65 new in-bound inquiries from prospective participants and for the inquiries to result in 20-25 new participants to help complete enrollment in the NIH-sponsored FIOC program.

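### The remote follow-up option does not except the triadic play task, and mode is neither recorded nor analysed, so the observed endpoints may not be measured alike and mode may differ by arm

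*Protocol*

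**What the plan says.** - Protocol, section 4, before the work plan: families may have "follow-ups and mentoring sessions in person or via the Microsoft Teams platform". No assessment task is excepted. The one extra step described for telehealth families concerns safety and comfort: "mothers will have an additional meeting with the resource person prior to the assessment".
- Protocol, section 4, item on observed coparenting during trilogue interaction: "All families are assessed at 3-months and at 12-months post-partum" in the LTP. The task has four parts, in which the parents change roles, and one of them is "c) all 3 family members play together".
- Protocol, section 4, item on infants' triangular capacities: "Gaze frequency and duration" are coded according to whether the infant looks at one parent, the other parent or neither. Affect and triangular bids are coded from the same recordings.
- Protocol, section 1: the first 150 families are allocated by urn randomization. After that, "The remaining families recruited up to 170 will be assigned to the experimental (FIOC) group".
- Protocol, section 1, describes the target parents as unmarried and not a couple, and section 11 speaks of parents who do not live together. Living apart is not an inclusion criterion in section 6.
- SAP, Primary Aims 1-4: t-tests, followed by models that adjust for unnamed confounders and for imbalance between arms. Assessment mode and enrolment period are not mentioned.

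**The concern.** The LTP is a standard situation, and its scores mean the same thing across families only if it is staged in the same way. With two parents on two screens, the three-together part no longer exists as defined, and an infant looking at the absent parent is looking at a device. The videotaped couple discussions are affected less, but they too change when two people talk over a link rather than in one room.

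Hypothesis 4 rests wholly on the LTP infant codes. Hypothesis 1 rests partly on LTP coparenting ratings and the couple-discussion ratings. If remote recordings are pooled with in-person ones, the least harm is added noise. If the remote share also differs between arms, part of the mode effect enters the arm comparison and looks like an effect of the intervention, or hides one. The SAP's general clause on confounding cannot repair this unless mode has been recorded, and neither document says that it is.

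**Working it through.** **1. The plan's own yardstick.** Protocol section 5 gives N = 120 (60 per arm), alpha .05, F(1,117) = 7.74 with d = .514 at 80% power, and F = 4.03 with d = .37 at 50% power.
- 2 × √(7.74/117) = 0.514 and 2 × √(4.03/117) = 0.371. Both stated d values reproduce.
- Power at d = .514 with 60 per arm is 0.797 (noncentral F) or 0.804 (normal approximation). At d = .37 it is 0.520 (noncentral F).

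These figures do not test the concern. They give the scale against which to read a bias.

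**2. Could the last families be seen when Teams is available?** The Teams text is in the July 2020 Protocol; its start date is not given. Appendix A dates a campaign to help complete enrolment from 23 October 2019 to 1 March 2020. Enrolment is prenatal, so a family recruited by it has its 12-month visit after 23 October 2020, later than the July 2020 version. Section 12 also describes consenting new participants by telehealth.

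**3. Imbalance in mode.** Assume a 75:75 split of the first 150 (no ratio is stated). Let q be the Teams share in families 1-150, the same in both arms, and r the share in families 151-170. Then

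Teams share in FIOC = (75q + 20r)/95, and in TAU = q.

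Bias in SD = (difference in share) × (mode effect in SD). The documents give no value for q, r or the mode effect; all are assumptions.

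| q | r | FIOC | TAU | Difference | Bias at 0.3 SD | Bias at 0.8 SD |
|---|---|---|---|---|---|---|
| 0 | 100% | 21.1% | 0% | 0.211 | 0.063 | 0.168 |
| 0 | 50% | 10.5% | 0% | 0.105 | 0.032 | 0.084 |
| 25% | 100% | 40.8% | 25% | 0.158 | 0.047 | 0.126 |
| 25% | 25% | 25% | 25% | 0 | 0 | 0 |
| 25% | 0 | 19.7% | 25% | -0.053 | -0.016 | -0.042 |

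If late families use Teams at least as often as the others, the size of the bias runs from 0 to about 0.17 SD. If they use it less often, the bias reverses slightly. The sign of the mode effect itself is unknown.

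**4. What the top of that range would do.** Suppose the shares carry over to 60 analysed per arm. The standard error of the standardised difference is √(2/60) = 0.183, so 0.168 SD is 0.92 standard errors. A nominal 5% two-sided test then rejects a true null about 15% of the time. If the shift works against FIOC, power at d = .514 falls from 80% to about 47%. At zero imbalance, neither changes through this route.

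**The case against.** The strongest reply is that Teams is offered without regard to arm: "All study participants will be offered the opportunity to be seen for initial assessments, follow-ups and mentoring sessions in person or via the Microsoft Teams". Among the 150 urn-randomized families nothing in the text makes mode depend on arm, although a choice made after assignment could. Earlier families of both arms with late 12-month visits could use Teams too, which dilutes any imbalance. The campaign target of "20-25 new participants to help complete enrollment" is a goal. It may count individuals rather than families, and it is not identified with families 151-170. All of this stands, so the link to arm is an inference from the order of enrolment.

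A reader might infer that the observed endpoints are in fact measured differently. The documents do not show that. Parents who live apart can still sit together with the baby on one camera, as an in-person LTP already requires them to meet. Section 13 also mentions scripted assessor instructions, in the context of debriefing, which are not reproduced. What remains is that the public plan does not secure comparable staging.

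A reader might also put the bias at 0.30 SD. That takes, for example, 60 analysed FIOC families that include all 20 late ones, all on Teams, with 10% Teams use elsewhere: (40 × 0.10 + 20)/60 = 40% against 10%, times a mode effect of 1.0 SD. It multiplies two extreme assumptions with no source in the documents, and I do not rely on it.

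The share-times-shift formula is also crude. It treats all Teams visits alike, although a triad together on camera may shift scores little, and a part that could not be run is missing data rather than a shifted score.

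Finally, the non-random allocation of families 151-170 is a separate and larger matter. This point concerns only how outcomes are recorded and should not be counted as the same defect.

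**Conclusion.** The concern holds as a gap in control of measurement. The Protocol permits remote follow-up without excepting a task that needs the triad together, and neither document provides for recording or analysing mode. Following the plan as written can pool recordings that are not comparable, and nobody could later show whether it had.

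The link to arm is a reasonable possibility, not an established fact. The imbalance in mode may be near zero or as much as about 21 points of enrolled families. The upper figure assumes a 75:75 split of the first 150, all late families on Teams and no one else. With assumed mode effects of 0.3 to 0.8 SD the bias is about 0 to 0.17 SD, in an unknown direction, against planned effects of .37 and .514. It should be corrected, chiefly because the remedy is cheap and a mode record is hard to rebuild afterwards.

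**What to change.** - Protocol, section 4: allow the LTP by Teams only when both parents and the infant are physically together on camera. Otherwise carry out the rest of the visit remotely and record the LTP as not done, with the reason.
- Visit form: record mode at every visit as in person, Teams together or Teams apart.
- SAP: tabulate mode and missing LTPs by arm and visit, and code infant gaze only from recordings with the triad together.
- SAP, sensitivity analyses of the LTP and couple-discussion comparisons: (a) in the 150 urn-randomized families, which removes the route through late FIOC-only enrolment; (b) in in-person recordings only. State that (b) is a subset selected after assignment and cannot replace the main comparison.

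The cost is one Protocol sentence, one form field and two short analyses. Some LTP scores will be lost, possibly more in FIOC, which is why missing LTPs need to be shown by arm. The in-person subset also has less power: starting from 60 per arm and d = .514 (80%, normal approximation), an equal loss of 10%, 20% or 30% leaves 54, 48 or 42 per arm and power of about 76%, 71% or 65%.
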